5.4.1. Cardiovascular Safety Stopping Criteria

1. New onset or worsening symptoms of cardiac ischemia which is reasonably attributable to GSK3039294
2. Development of decompensated or uncontrolled cardiac failure which is reasonably attributable to GSK303294.
3. Systolic blood pressure > 170 mmHg as an average of triplicate readings taken at rest over 15 minutes on three consecutive days at any time after administration and is reasonably attributable to GSK3039294.
4. **Healthy Volunteers & Amyloidosis Patients without bundle branch block:** QTcF > 500 msec, (or a change from baseline of QTcF > 60 msec on a 12-lead

ECG in healthy volunteers) which is reasonably attributable to GSK3039294 on an average from triplicate readings (see Section 5.4.3).

5. **Systemic Amyloidosis patients with bundle branch block** - if baseline QTcF < 450 msec: QTcF > 500 msec on a 12-lead ECG at any time after administration of GSK3039294; If baseline QTcF 450-480 msec: QTcF > 530 msec at any time after drug administration and is reasonably attributable to GSK3039294, as an average of triplicate readings (see Section 5.4.3).
6. Any cardiovascular SAE as predefined in [Appendix 4](#) after drug administration and is reasonably attributable to GSK3039294

Please also see Section 5.4.4. Cardiac Arrhythmia stopping criteria

[figure not shown]
5.4.2. Liver Chemistry Stopping Criteria

Liver chemistry stopping and increased monitoring criteria have been designed to assure subject safety and evaluate liver event etiology (in alignment with the FDA premarketing clinical liver safety guidance).

<http://www.fda.gov/downloads/Drugs/GuidanceComplianceRegulatoryInformation/Guidances/UCM174090.pdf>

Study treatment will be discontinued **for a healthy volunteer subject in Part A or B, or a systemic amyloidosis patient without liver involvement /no biochemical liver dysfunction in Part C** with baseline liver chemistry within the normal reference range for ALT if they are reasonably attributable to GSK3039294 and provided the following liver chemistry stopping criteria are met:

Phase I Liver Chemistry Stopping Criteria – Liver Stopping Event Algorithm

In Part C, systemic amyloidosis patients will be required to return for follow-up liver chemistry assessments within 1 week of the changes from the baseline liver chemistry at Day -1 (see [Table 6](#)) being reported. Individual systemic amyloidosis patients will be withdrawn from the study if the following liver chemistry changes are reported from baseline at Day -1 (see [Table 6](#)).

Table 6 Change from baseline in liver chemistry for repeat or withdrawal

Baseline Liver Chemistry	Repeat assessment within 1 week	Withdrawal
x1 ULN < ALT ≤ x3 ULN Bilirubin ≤ x1ULN	ALT > x4 ULN Bilirubin > x 1.5 ULN	ALT > x6 ULN Bilirubin > x 1.5 ULN
x1 ULN < ALT ≤ x3 ULN Bilirubin ≤ x1.5 ULN	ALT > x4 ULN Bilirubin > x 2 ULN	ALT > x6 ULN Bilirubin > x 2 ULN

Liver Safety Required Actions and Follow up Assessments Section can be found in [Appendix 2](#) (Section 12.2)

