12.2. Appendix 2: Liver Safety Required Actions and Follow up Assessments

Phase I Liver chemistry stopping criteria have been designed to assure subject safety and to evaluate liver event etiology (in alignment with the FDA premarketing clinical liver safety guidance).

<http://www.fda.gov/downloads/Drugs/GuidanceComplianceRegulatoryInformation/Guidances/UCM174090.pdf>.

12.2.1. Healthy Volunteers:

Phase I liver chemistry stopping criteria and required follow up assessments

Liver Chemistry Stopping Criteria – Liver Stopping Event	
ALT-absolute	
ALT\geq3xULN
 
If ALT\geq3xULN AND bilirubin^{1,2} \geq 2xULN (>35% direct bilirubin) or INR >1.5, Report as an SAE.
 
See additional Actions and Follow Up Assessments listed below

Required Actions and Follow up Assessments following Liver Stopping Event	
Actions	Follow Up Assessments

 • Immediately discontinue study treatment • Report the event to GSK within 24 hours • Complete the liver event CRF, and complete an SAE data collection tool if the event also meets the criteria for an SAE² • Perform liver event follow up assessments • Monitor the subject until liver chemistries resolve, stabilise, or return to within baseline (see MONITORING below) 
MONITORING:
 
If ALT\geq3xULN AND bilirubin \geq 2xULN or INR >1.5
 
 • Repeat liver chemistries (include ALT, AST, alkaline phosphatase, bilirubin) and perform liver event follow up assessments within 24 hrs • Monitor subjects twice weekly until liver chemistries resolve, stabilise or return to 	
 • Viral hepatitis serology³ • Blood sample for pharmacokinetic (PK) analysis, obtained within 48 hours of last dose⁴ • Serum creatine phosphokinase (CPK) and lactate dehydrogenase (LDH). • Fractionate bilirubin, if total bilirubin\geq2xULN • Obtain complete blood count with differential to assess eosinophilia • Record the appearance or worsening of clinical symptoms of liver injury, or hypersensitivity, on the AE report form • Record use of concomitant medications on the concomitant medications report form including acetaminophen, herbal remedies, other over the counter medications. • Record alcohol use on the liver event

Liver Chemistry Stopping Criteria – Liver Stopping Event	

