
within baseline
 
 A specialist or hepatology consultation is recommended 
If ALT ≥ 3xULN AND bilirubin < 2xULN and INR ≤ 1.5:
 
 Repeat liver chemistries (include ALT, AST, alkaline phosphatase, bilirubin) and perform liver event follow up assessments within 24-72hrs Monitor subjects weekly until liver chemistries resolve, stabilize or return to within baseline 	
alcohol intake case report form
 
If ALT ≥ 3xULN AND bilirubin ≥ 2xULN or INR > 1.5:
 
 Anti-nuclear antibody, anti-smooth muscle antibody, Type 1 anti-liver kidney microsomal antibodies, and quantitative total immunoglobulin G (IgG or gamma globulins). Serum acetaminophen adduct HPLC assay (quantifies potential acetaminophen contribution to liver injury in subjects with definite or likely acetaminophen use in the preceding week [James, 2009]. NOTE: not required in China. Liver imaging (ultrasound, magnetic resonance, or computerised tomography) and /or liver biopsy to evaluate liver disease; complete Liver Imaging and/or Liver Biopsy CRF forms.

- Serum bilirubin fractionation should be performed if testing is available. If serum bilirubin fractionation is not immediately available, discontinue study treatment for that subject if ALT ≥ 3xULN and bilirubin ≥ 2xULN. Additionally, if serum bilirubin fractionation testing is unavailable, **record presence of detectable urinary bilirubin on dipstick**, indicating direct bilirubin elevations and suggesting liver injury.
- All events of ALT ≥ 3xULN and bilirubin ≥ 2xULN (>35% direct bilirubin) or ALT ≥ 3xULN and INR > 1.5, if INR measured, which may indicate severe liver injury (possible 'Hy's Law'), **must be reported as an SAE (excluding studies of hepatic impairment or cirrhosis)**; INR measurement is not required and the threshold value stated will not apply to subjects receiving anticoagulants
- Includes: Hepatitis A IgM antibody; Hepatitis B surface antigen and Hepatitis B Core Antibody (IgM); Hepatitis C RNA; Cytomegalovirus IgM antibody; Epstein-Barr viral capsid antigen IgM antibody (or if unavailable, obtain heterophile antibody or monospot testing); Hepatitis E IgM antibody

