
 • Repeat liver chemistries (include ALT, AST, alkaline phosphatase, bilirubin) and perform liver event follow up assessments within 24-72 hrs • Monitor subjects weekly until liver chemistries resolve, stabilize or return to within baseline 	
 • Serum acetaminophen adduct HPLC assay (quantifies potential acetaminophen contribution to liver injury in subjects with definite or likely acetaminophen use in the preceding week [James, 2009]). NOTE: not required in China • Liver imaging (ultrasound, magnetic resonance, or computerised tomography) and /or liver biopsy to evaluate liver disease: complete Liver Imaging and/or Liver Biopsy CRF forms.

1. Serum bilirubin fractionation should be performed if testing is available. If serum bilirubin fractionation is not immediately available, discontinue study treatment for that subject if ALT \geq 3xULN **and** bilirubin \geq 2xULN. Additionally, if serum bilirubin fractionation testing is unavailable, **record presence of detectable urinary bilirubin on dipstick**, indicating direct bilirubin elevations and suggesting liver injury.
2. All events of ALT \geq 3xULN and bilirubin \geq 2xULN (>35% direct bilirubin) or ALT \geq 3xULN and INR > 1.5, if INR measured, which may indicate severe liver injury (possible 'Hy's Law'), must be reported as an SAE (excluding studies of hepatic impairment or cirrhosis); INR measurement is not required and the threshold value stated will not apply to subjects receiving anticoagulants
3. Includes: Hepatitis A IgM antibody; Hepatitis B surface antigen and Hepatitis B Core Antibody (IgM); Hepatitis CRNA; Cytomegalovirus IgM antibody; Epstein-Barr viral capsid antigen IgM antibody (or if unavailable, obtain heterophile antibody or monospot testing); Hepatitis E IgM antibody
4. PK sample may not be required for subjects known to be receiving placebo or non-GSK comparator treatments. Record the date/time of the PK blood sample draw and the date/time of the last dose of study treatment prior to blood sample draw on the CRF. If the date or time of the last dose is unclear, provide the subject's best approximation. If the date/time of the last dose cannot be approximated OR a PK sample cannot be collected in the time period indicated above, do not obtain a PK sample. Instructions for sample handling and shipping are in the SRM

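### For subjects with normal baseline ALT, Section 5.4.2 makes the liver stop depend on attribution to study drug; Appendix 2 requires it at ALT ≥3xULN regardless, and nothing says which prevails

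*Protocol*

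**What the plan says.** Section 5.4.2 opens with the rule for healthy volunteers in Parts A and B, and for Part C patients without liver involvement whose baseline ALT is in the normal range. Their treatment is discontinued "if they are reasonably attributable to GSK3039294 and provided the following liver chemistry stopping criteria are met". Both conditions have to hold. The algorithm that follows is a figure and is not shown in the text available. The same section then gives Table 6, a withdrawal rule for Part C patients with baseline ALT above 1xULN and up to 3xULN; that rule has no attribution condition. The section closes with a pointer: "Liver Safety Required Actions and Follow up Assessments Section can be found in" Appendix 2.

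Appendix 2 states a criterion of its own. In 12.2.1 (healthy volunteers) and again in 12.2.2 (patients), the liver stopping event is ALT ≥3xULN. Under "Required Actions and Follow up Assessments following Liver Stopping Event" the first action is "Immediately discontinue study treatment", followed by "Report the event to GSK within 24 hours". The tests that look for a cause, beginning with "Viral hepatitis serology", stand in the follow-up column of the same table. An ALT rise with bilirubin <2xULN and INR ≤1.5 is handled as the same stopping event; for it, staff repeat the chemistry and "perform liver event follow up assessments within 24-72hrs" (12.2.2 says the same).

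**The concern.** A stopping rule should give one answer for one laboratory result. Here the main text adds a causality judgement that the detailed procedure does not have.

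The order also differs. In Appendix 2 the drug is stopped and the cause is then investigated. In Section 5.4.2 the stop depends on a judgement that those investigations are meant to inform. The nearest definition, in Section 12.4.4, sets a fairly high bar: positive evidence or argument for a causal link is needed, and being unable to exclude one is not enough. A new, unexplained ALT rise may not meet that bar on the day it is reported.

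At stake is whether stopping is mandatory or left to the investigator's general power to withdraw subjects (Section 5.4), in a study where Section 4.6.2 expects no medical benefit for participants.

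**Working it through.** The plan gives no figure to reproduce, and no arithmetic applies. The check is a comparison of the two rules, case by case, for a subject in the group that the first sentence of Section 5.4.2 covers. It assumes that the algorithm not shown uses the Appendix 2 threshold of ALT ≥3xULN. Section 12.4.2 defines an SAE-level liver event as ALT ≥3xULN with either total bilirubin ≥2xULN (more than 35% direct, or fractionation unavailable) or INR >1.5.

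- **Judged attributable, any bilirubin or INR.** Section 5.4.2: stop required. Appendix 2: stop required. They agree.
- **Judged unrelated, SAE-level.** Appendix 2: stop required. Section 5.4.2 alone: not required. Section 5.4, however, withdraws a subject for an SAE, so the outcome is the same. Section 5.4 names Appendix 3 (genetics) for the SAE definition, which is in fact in Appendix 4; the intent is clear.
- **Judged unrelated, bilirubin <2xULN and INR ≤1.5.** Appendix 2: stop required. Section 5.4.2: not required. They differ.
- **Judged unrelated, bilirubin ≥2xULN with a measured direct fraction of 35% or less, and INR ≤1.5.** This is not an SAE under the liver item of 12.4.2. Appendix 2: stop required, because ALT alone triggers it. Section 5.4.2: not required. They differ.

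The difference therefore covers every ALT ≥3xULN judged unrelated that is not SAE-level, and not only the isolated ALT rise.

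Next, does any text settle the matter?

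- The closing line of Section 5.4.2 refers to Appendix 2 for actions and follow-up. It does not withdraw the attribution condition.
- The note under Table 7 sends the reader to Section 6 and Appendix 2 for the criteria. Section 6 holds no liver rule.
- Section 5.4.2.1 bars restart or rechallenge once the criteria are met. It has no attribution test and sits more easily with Appendix 2, but it does not say which rule prevails.
- The algorithm cannot be inspected. The attribution condition stands in the sentence that introduces it, as a requirement additional to whatever criteria the algorithm contains.

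**The case against.** The strongest reply is that a site following both sections always stops. Section 5.4.2 says when treatment is discontinued; it is silent on rises judged unrelated. Appendix 2 supplies an unconditional instruction, Section 5.4.2 refers to it, and Section 7 allows no waivers except for immediate safety concerns. The investigator may also withdraw anyone for safety at any time.

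Most of this stands. A reader might infer that the two texts give opposite instructions, or that Section 5.4.2 permits dosing to continue after an unrelated ALT rise. The documents do not support either reading: one text requires the stop and the other does not require it. What the reply does not remove is the explicit condition in the main stopping section. An investigator who reads the appendix as describing what to do once Section 5.4.2 has been met would have grounds for thinking the stop is not mandatory, and no sentence corrects that reading.

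A second reply is that attribution is used throughout the individual stopping rules, for example in Sections 5.4.1 and 5.4.5. That is so. For liver chemistry, though, the protocol's own detailed procedure leaves it out, as does Table 6 within the same section, so the two liver texts still need reconciling.

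A third is that the missing algorithm might restate an unconditional stop. That cannot be excluded. It would add a further inconsistency with its own lead-in sentence; it would not remove the condition.

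**Conclusion.** The inconsistency is real and narrow. It concerns healthy volunteers, and Part C patients with normal baseline ALT and no liver involvement, and it arises only for ALT ≥3xULN judged unrelated and not SAE-level. It should not be read as applying to all of Section 5.4.2, because Table 6 carries no attribution condition.

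No numerical size can be given. The documents state no rate of ALT ≥3xULN judged unrelated. It is also tempting to infer a number of extra dosing days, but Appendix 2 requires reporting to the sponsor within 24 hours and repeat chemistry within 24 to 72 hours or sooner, so no such count is supported. Adverse event counts are not affected.

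The conclusion rests on the visible wording and on the assumption above about the algorithm's threshold. The cross-reference to the stricter text makes harm less likely. The point is still worth fixing, because it concerns a mandatory safety stop and the repair is one clause.

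**What to change.** In the first rule of Section 5.4.2, delete the attribution condition, that is, the words of the quoted clause up to and including *and*, so that discontinuation follows whenever the listed liver chemistry criteria are met. For this group the stop would then not depend on attribution, in line with Appendix 2 and with the restart ban in 5.4.2.1. Sections 12.2.1 and 12.2.2 need no change for this point.

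The cost is a wording change in the protocol. The small downside is that an occasional subject whose ALT rise has another cause will be discontinued and replaced; Section 4.3 already allows replacement.

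This edit does not deal with Part C patients whose baseline ALT is raised. Table 6 sets their withdrawal at ALT >6xULN with raised bilirubin, while 12.2.2 stops patients at ALT ≥3xULN. That is a separate conflict and needs its own sentence on scope or precedence.

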5.4.2.1. Study Treatment Restart or Rechallenge

Study treatment restart or rechallenge after liver chemistry stopping criteria are met by any subject participating in this study is not allowed.

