
 • Immediately discontinue study treatment • Report the event to GSK within 24 hours • Complete the liver event CRF, and complete an SAE data collection tool if the event also meets the criteria for an SAE² • Perform liver event follow up assessments • Monitor the subject until liver chemistries resolve, stabilise, or return to within baseline (see MONITORING below) • Do not restart/rechallenge subject with study treatment. Permanently discontinue study treatment and may continue subject in the study for any protocol specified follow up assessments 
MONITORING:
 
If ALT\geq3xULN AND bilirubin \geq 2xULN or INR >1.5:
 
 • Repeat liver chemistries (include ALT, AST, alkaline phosphatase, bilirubin) and perform liver event follow up assessments within 24 hrs • Monitor subjects twice weekly until liver chemistries resolve, stabilise or return to within baseline • A specialist or hepatology consultation is recommended 
If ALT\geq3xULN AND bilirubin < 2xULN and INR \leq1.5:
	
 • Viral hepatitis serology³ • Blood sample for pharmacokinetic (PK) analysis, obtained within 48 hours of last dose⁴ • Serum creatine phosphokinase (CPK) and lactate dehydrogenase (LDH). • Fractionate bilirubin, if total bilirubin\geq2xULN • Obtain complete blood count with differential to assess eosinophilia • Record the appearance or worsening of clinical symptoms of liver injury, or hypersensitivity, on the AE report form • Record use of concomitant medications on the concomitant medications report form including acetaminophen, herbal remedies, other over the counter medications. • Record alcohol use on the liver event alcohol intake case report form 
If ALT\geq3xULN AND bilirubin \geq 2xULN or INR >1.5:
 
 • Anti-nuclear antibody, anti-smooth muscle antibody, Type 1 anti-liver kidney microsomal antibodies, and quantitative total immunoglobulin G (IgG or gamma globulins).

Liver Chemistry Stopping Criteria – Liver Stopping Event	

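### Section 12.2.2 stops study drug permanently at any ALT of 3xULN or more, without the baseline limit that Section 5.4.2 and Table 6 apply to Part C patients entering with raised ALT

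*Protocol*

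**What the plan says.** Section 5.1 (additional inclusion criteria for patients) allows ALT up to and including 3xULN and expects some patients with a large liver amyloid load.

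Section 5.4.2 then gives two routes. The standard stopping algorithm covers healthy volunteers and, in Part C, a "systemic amyloidosis patient without liver involvement /no biochemical liver dysfunction", in each case "with baseline liver chemistry within the normal reference range for ALT" and only if the change is reasonably attributable to the drug. Table 6 has two rows, both for Day -1 ALT above 1 and up to 3xULN. ALT above 4xULN falls under "Repeat assessment within 1 week". The withdrawal cell of the first row reads "ALT > x6 ULN Bilirubin > x 1.5 ULN", and the second row has the same ALT limit with bilirubin above 2xULN. The lead-in is "Individual systemic amyloidosis patients will be withdrawn from the study if the following liver chemistry changes are reported from baseline at Day -1". Directly after Table 6, the section refers the reader to Appendix 2.

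In Appendix 2, Section 12.2.2 (Patients) defines a liver stopping event as an absolute ALT of 3xULN or more. The required actions are "Immediately discontinue study treatment" and then "Permanently discontinue study treatment and may continue subject in the study for any protocol specified follow up assessments". If bilirubin is below 2xULN and INR is 1.5 or less, chemistry is repeated in 24 to 72 hours. The section does not mention baseline ALT, liver involvement, attribution to drug, or Table 6.

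**The concern.** A site managing a Part C patient with raised Day -1 ALT finds two different instructions for the same on-study reading, and Section 5.4.2 itself leads from Table 6 to the unqualified rule.

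If the site follows Section 12.2.2, a patient who was eligible with ALT near 3xULN can lose the drug after little or no rise. That cannot be reversed, because Section 5.4.2.1 states: "Study treatment restart or rechallenge after liver chemistry stopping criteria are met by any subject participating in this study is not allowed". That patient's remaining on-treatment SAP and PK data up to Day 21 are lost too. If the site follows Table 6, dosing continues after what Section 12.2.2 calls a liver stopping event. In a study that offers patients no medical benefit (Section 4.6.2), the stopping threshold should not depend on which page is consulted.

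**Working it through.** No plan figure has to be reproduced. The check sets the rules side by side for one patient type.

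**Inputs**
- Day -1 ALT above 1 and up to 3xULN: permitted by Section 5.1 and covered by Table 6.
- Table 6 ALT limits: above 4xULN for a repeat, above 6xULN for withdrawal.
- Section 12.2.2 ALT limit: 3xULN or more, at any baseline.
- Assumption for illustration: bilirubin stays at 1.0xULN, below every bilirubin limit in Table 6, and INR is not raised.

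Table 6 lists ALT and bilirubin limits in the same cell without saying whether either or both must be exceeded, so both readings are shown.

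| On-study ALT (xULN) | Table 6, either limit suffices (OR) | Table 6, both limits needed (AND) | Section 12.2.2 |
|---|---|---|---|
| 3 to 4 | no action | no action | permanent drug stop |
| above 4 to 6 | repeat within 1 week | no action | permanent drug stop, repeat in 24 to 72 hours |
| above 6 | withdrawal | no action | permanent drug stop, repeat in 24 to 72 hours |

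**Results**
- Under OR, the conflict runs from 3 to 6xULN and closes above 6xULN. If bilirubin exceeds its Table 6 limit, that alone triggers withdrawal and the conflict disappears.
- Under AND, the conflict also starts at 3xULN but has no upper end while bilirubin stays within its limit. If bilirubin exceeds its limit, the conflict again runs from 3 to 6xULN.
- The band is therefore 3xULN to at least 6xULN whenever bilirubin is within its Table 6 limit.
- At the boundary, Day -1 ALT of exactly 3.0xULN satisfies the entry limit (3 ≤ 3) and already meets the Section 12.2.2 stop (3 ≥ 3).
- Patients with normal Day -1 ALT have no such conflict, because Table 6 has no row for them.

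**Which rule was meant.** The Section 5.4.2 scope sentence limits the standard algorithm to normal baseline ALT, and Table 6 takes up where it ends. The natural reading is that the 3xULN stop is for normal baselines and Table 6 is for raised ones. Section 12.2.2 has its own heading for patients and its own threshold, and it does not carry that limit. The algorithm figure in Section 5.4.2 is not shown in the text at hand. The comparison does not need it, because both conflicting rules are readable.

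**The case against.** The strongest defence is that Section 5.4.2 is the governing section, its scope sentence makes the intent plain, and Appendix 2 is cited there only for required actions and follow-up. This stands as evidence of intent. It does not cure the text, because Section 12.2.2 also presents itself as stopping criteria and states a threshold.

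Second, the two texts govern different acts. Section 12.2.2 stops drug and lets the patient stay in the study for follow-up, while Table 6 governs withdrawal from the study. A reader might infer that the rules cannot both be obeyed. The documents do not support that: stopping drug at 3xULN complies with both. But doing so leaves the baseline limit in Section 5.4.2 and the repeat step above 4xULN without purpose.

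Third, a reader might infer that Table 6 lets a patient go a full week unmonitored with a high ALT. That goes too far. Patients are in-patient until Day 8, the Section 7.1.5 schedule appears to place safety laboratory tests at several out-patient visits before Day 21, and Section 5.4 lets the investigator withdraw a subject at any time for a valid clinical reason.

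Fourth, the effect on the data is small. Section 9.3.1 keeps patients in the PK and PD populations on the data collected before the stop, and Section 4.3 permits replacement. This stands.

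**Conclusion.** The inconsistency is real and should be fixed. For Part C patients with Day -1 ALT above 1 and up to 3xULN, Sections 5.4.2 and 12.2.2 prescribe different actions from 3xULN up to at least 6xULN, provided bilirubin is within its Table 6 limit. The upper end is exactly 6xULN only if exceeding the ALT limit alone is enough in Table 6, and the protocol does not settle that.

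A reader might go on to infer a material loss of patients or a biased SAP result. The documents do not support this. The protocol gives no number or proportion of the planned minimum of 12 patients who would have raised ALT, so no affected fraction can be stated. The point is about a clear and consistent safety rule.

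**What to change.** **Section 12.2.2.** State that the isolated stop at ALT of 3xULN or more applies to patients whose Day -1 ALT is normal, with or without liver involvement, and that patients with Day -1 ALT above 1 and up to 3xULN follow Table 6. Keep ALT of 3xULN or more together with bilirubin of 2xULN or more (over 35% direct, or fractionation unavailable), or with INR above 1.5, as a stop and an SAE for all patients.

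**Section 5.4.2.** Make the matching edit so that both sections share the same scope. The words on liver involvement matter because a patient with liver amyloid and normal ALT has no Table 6 row, and the slash in the present scope sentence leaves it unclear whether the standard algorithm covers that patient. Use the same attribution condition in both sections. At present Section 5.4.2 requires attribution to drug for the standard algorithm and Section 12.2.2 does not.

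**Table 6.** State that ALT above 6xULN alone triggers withdrawal.

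The cost is a few sentences of protocol wording. Sample size, endpoints and analysis are unchanged.
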